The primary objective is to understand how many people end up pregnant by using the at-home insemination Mosie

Kit during up to 6 cycles of voluntary use and how many people get pregnant using the Mosie Kit without using sex because they are either single, in a same-sex relationship, or in an unconsumated mariage due to infertility problems. The secondary objectives are to understand perceived safety and ease of use of the at-home Mosie Kit.The

tertiary objective will be to examine pregnancy outcome in relationship to self-reported reason for infertility. Additionally, since COVID-19 has recently affected

everyone, its effect on family expansion plans and stress

will also be examined.

Endpoints*: The specific study endpoints include pregnancy rates after

up to 6 cycles of at-home intracervical insemination (ICI),

perceived ease of use, perceived safety, and the

relationship of infertility source with pregnancy outcome rates, stress related to COVID-19 and its impact on family

expansion plans.

Study Population: The sample will be drawn from all people who have

purchased an at-home Mosie Kit in the past 2-8 full months

prior to the study commencement. The approximate

sample size will be 500 but all will be invited to participate.

Objectives:

MOSIE-001

Both females and males will be included in the study. It is expected that the age range of the participants will vary from approximately 21 - 50 years of age. The participants will have a history of fertility problems, specifically problems getting pregnant. Otherwise, the participants should be in overall good health. No other health conditions are being used as exclusion criteria for participation in the study. Participants may be located anywhere in the world as this study will be conducted using an online web-based survey.

Phase or Stage:

This is a post-market retrospective study to examine the experience people have with using the Mosie Kit for at-home insemination.

Description of Sites/Facilities Enrolling Participants:

No sites or facilities will be used in this study. Participants will be existing Mosie Baby Clients who have purchased a Mosie Kit in the prior 8 months. Participants may reside anywhere in the world.

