Since [name] sperm freezing success in 1953 with a subsequent live birth, collecting and using sperm for insemination in humans was made possible. However, it would be more than a decade before it became legally possible as it was initially ruled as contrary to public policy and good morals. In the 1960s and 70s, sperm selection and washing techniques led to Intrauterine insemination (IUI) which placed the sperm even further into the woman's body by putting it directly into the uterus. By the 1970s sperm banks in the US became popular. Also in the 1970s, Steptoe and Edwards introduced the world to In-Vitro Fertilization (IVF). More recently, techniques such as intratubal insemination, and intraperitoneal insemination have been added to the available conception methods. During the last decades the popularity of Intrauterine Insemination (IUI) increased because it was safer, painless, and more cost-effective. Additionally, more information has become available about sperm selection techniques and now there is a greater understanding of many of the causes of infertility.

The most popular method of insemination is to use the husband's sperm (Artificial Insemination by Homologous or Husband (AIH)). In some cases anonymous donor sperm is used. Intracervical (ICI) or intravaginal insemination (IVI) are terms used interchangeably to describe the insemination technique colloquially known as the "turkey baster method". This method consists of placing the semen into the vagina at or near the cervix. In the United States, IUI is the most frequently doctor assisted technique. Some researchers have examined the success rates of each technique. ICI/IVI has been found to have a per cycle pregnancy rate of 10-15% while IUI has been found to be slightly higher up to 10-35%. Meanwhile techniques such as IVF can be as high as 31% in people under 35 years of age and as low as 3% for those above 43 according to the CDC.

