3 OBJECTIVES AND ENDPOINTS

OBJECTIVES	ENDPOINTS	JUSTIFICATION FOR ENDPOINTS	PUTATIVE MECHANISMS OF ACTION
Primary			
The primary objective is to understand the outcome of using the at-home intracervical insemination Mosie kit, i.e. pregnancy rate after its use.	The primary endpoints is: Pregnancy Rate after up to 6 cycles. Another primary end point is to understand the rates of pregnancy in people who desire to get pregnant without intercourse (i.e. both single and those in LGBTQ relationships.	The ultimate objective of using the Mosie Kit is to end up pregnant. Thus pregnancy rate is a primary endpoint. Specifically, pregnancy rate in up to 6 (six) cycles will be examined as it is the typical standard timeframe for attempting to get pregnant using IVI or IUI before seeking an alternative method. People who have no known fertility issue who are trying to conceive without intercourse such as those who are in LGBTQ relationships or those who are not in any relationship at all will likely have higher pregnancy rates than those with known fertility issues of female origin. Women in LGBTQ relationships wishing to conceive might also have a higher pregnancy rate than those in heterosexual relationships where infertility might be caused by things like low sperm count, sperm motility issues or erectile dysfunction (ED).	The Mosie Kit is intended to be used to deposit semen at or near the cervix where the sperm will have an increased likelihood of entering the uterus and pairing up with the ovum resulting in a pregnancy. Pregnancy rates increase when sperm reaches the ovum and fertilizes it. In people with no known fertility issues, the Mosie kit deposits the semen where it is able to fertilize the ovum. People without infertility issues who want to get pregnant without sex by using the Mosie Baby are also more likely than people with known fertility issues to get pregnant.

Secondary			

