This study does not use randomization. While no control group will be examined for the study, determining the result of some of the hypotheses is based on using the reported pregnancy rate of IUI in the literature. Specifically, the reported rate of pregnancy with IUI is as high as 20% in one cycle according to the American Pregnancy Association. According to the CDC, it can range between 10-35% across 6 cycles.

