5 STUDY POPULATION

The study population will consist of all individuals who have purchased the Mosie Kit in the past 2-8 complete months prior to study initiation. All qualifying individuals will receive an invitation to participate. These individuals will typically be of child-bearing age, both females and males, and generally ages ranging 18-50 years old.

It is assumed that purchasing the Mosie Kit means the kit will be used as intended for at-home insemination. One of the inclusion criteria is to have previously used the kit. Therefore, the initial list of study participants will be drawn from people who have placed a purchase order within the prior 8 complete months; complete months are used with the expectation that the Mosie Kit would be used within the month post-purchase. If the study duration is expanded, additional potential participants will be invited who have purchased the kit at least 2 full months prior to being invited to participate in the study.

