9.1 Statistical Hypotheses and General Statistical Approach

The primary objective is to understand the outcome of using the Mosie kit for Intracervical insemination, i.e. pregnancy rate after its use. Specifically the hypothesis is as follows.

Primary hypothesis 1: Pregnancy rates using the at-home insemination Mosie Kit to deposit semen near or at the cervix (i.e. intracervical insemination) are equivalent or better than traditional in doctor's office intrauterine insemination (IUI). Conversely the null hypothesis is that the pregnancy rates using the at-home insemination Mosie Kit to deposit semen near or at the cervix do not have higher rates of pregnancy than in doctor's office IUI.

Analysis: Comparison of total rates of pregnancy using the Mosie Kit to the 10-20% rate reported for IUI by the American Pregnancy Association.

Primary Hypothesis 2: Pregnancy rates of LGBTQ couples or single women using the Mosie Kit where the female has no know fertility issues will be higher than that of heterosexual couples with a known fertility cause or those that are designated as having an unexplained fertility issue. The alternative hypothesis is that people with no known

fertility issues using the Mosie Kit will have less pregnancies than heterosexual couples with known fertility issues.

Analysis: Rate of pregnancy using the Mosie Kit will be obtained for the following groups: LGBTQ couples where carrying female has no known fertility issues, LGBTQ couples where carrying female has a known fertility issue, Heterosexual people with no known fertility issue, Heterosexual people with a known fertility issue, Single females with no known fertility issue and Single females with a known fertility issue. The rates of each group will be analyzed using descriptive statistics and the aggregate of the 3 groups with fertility issues will be compared with the aggregate of the 3 groups without fertility issues. An ANOVA will be used to compare the differences between groups.

Secondary Hypothesis 1: The participants perceived the Mosie Kit to be easy to use for its intended purpose. The alternative hypothesis is that the participants perceive the Mosie Kit to be difficult to use for its intended purpose.

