9.4.3 Exploratory Analyses

Additional exploratory data analysis will be conducted to examine the main characteristics of the data. This analysis will be done using descriptive statistics, scatter plots, and odds ratio. If the exploratory analysis warrants the testing of new hypotheses, t-test or ANOVA may be used for further analysis.

Exploratory modeling will be conducted to examine multiple variables and their relationship to the pregnancy outcome. This will include the source of infertility, age, number of inseminations, number of cycles, lying time, and type of relationship. The model will use correlations and goodness of fit tests in its analysis.

1 0 SUPPORTING DOCUMENTATION AND OPERATIONAL CONSIDERATIONS

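### Primary hypothesis 1 appears to compare a per-person pregnancy total over up to 6 cycles with an IUI rate whose 20% end is a one-cycle figure; against that figure, any use beyond one cycle favours the kit, by an amount the documents leave open

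*Combined protocol and SAP*

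**What the plan says.** The objectives table in section 3 states: "The primary endpoints is: Pregnancy Rate after up to 6 cycles". The Synopsis (section 1.1) likewise counts people who become pregnant over up to 6 cycles. In Appendix A the visible outcome item is a single yes/no on whether using the kit led to a pregnancy, with no cycle limit.

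Section 9.1 gives the whole analysis of primary hypothesis 1 as "Comparison of total rates of pregnancy using the Mosie Kit to the 10-20% rate reported for IUI by the American Pregnancy Association". It names no test, no reference value within 10-20% and no margin, although the hypothesis is that the kit is equivalent to or better than IUI. Section 9.4.1 sets 0.05 and one-tailed testing for directional hypotheses.

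Section 4.1 says of the same source that "the reported rate of pregnancy with IUI is as high as 20% in one cycle according to the American Pregnancy Association". It then adds a second benchmark that section 9.1 does not use: "According to the CDC, it can range between 10-35% across 6 cycles". Section 2.2 puts the same range in a per-cycle sentence, giving ICI "a per cycle pregnancy rate of 10-15% while IUI has been found to be slightly higher up to 10-35" percent.

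The number of cycles enters only the exploratory model of section 9.4.3: "This will include the source of infertility, age, number of inseminations, number of cycles, lying time, and type of relationship".

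**The concern.** A person who tries several cycles has several chances to conceive. Setting the share of people who ever conceived against the chance of conceiving in one IUI cycle gives the kit credit for exposure that the reference does not have. The answer to primary hypothesis 1 would then depend partly on how many cycles respondents used.

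This matters because section 2.2 leaves the question open: one cited crossover study found IUI better than ICI (15% against 9%), while a cited review found the evidence insufficient. Section 2.3.2 says the results will inform users how the kit compares with IUI, and section 10.1.3 allows aggregate results in marketing. A difference of units should not settle the matter.

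**Working it through.** **The plan's own figure.** Section 9.2 gives ±4.4% for 500 surveys and ±5% for 384. The formula 1.96 × √(0.25/n) gives 4.38% and 5.00%. Both reproduce; they concern precision only and do not touch the unit question.

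**Direction.** Pregnancies/people = (pregnancies/cycles) × (cycles/people). The last factor is the mean number of cycles used, between 1 and 6, so the total matches the per-cycle rate only if everyone used one cycle. The direction does not need a constant conception rate: the share who ever conceived cannot be smaller than the share who conceived in cycle 1.

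**Inputs for an illustration.** n = 500 (section 9.2); one-sided 0.05 (section 9.4.1); reference 20% (section 4.1). The exact binomial test is my choice. It declares the kit better at 116 or more pregnancies (23.2%), with true size 0.043. The mixes of planned cycles are assumptions, with stopping at conception.

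**Formulas.** Total = Σ shareₖ × (1 − Sₖ), where Sₖ is the chance of no pregnancy in k cycles.
- Constant rate r: Sₖ = (1 − r)ᵏ.
- Users who differ in fertility, with r distributed Beta(a, b): Sₖ is the product over j = 0 to k−1 of (b + j)/(a + b + j). I take a + b = 5, an assumed spread. At a mean of 20% this is Beta(1,4), with Sₖ = 4/(4 + k).

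**A kit at exactly 20% per cycle.**

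| Planned cycles | Constant: total, P(declared better) | Beta(1,4): total, P |
|---|---|---|
| All one | 20.0%, 0.04 | 20.0%, 0.04 |
| 80% one, 20% two | 23.2%, 0.52 | 22.7%, 0.40 |
| 60/20/10/5/3/2% for 1-6 | 30.5%, >0.99 | 28.3%, >0.99 |

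For example, 0.8 × 20% + 0.2 × 36% = 23.2%; with the Beta spread, 0.8 × 20% + 0.2 × 33.3% = 22.7%.

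**Kits below 20%.** These depend heavily on the assumptions. The window mix reflects that the population is "all individuals who have purchased the Mosie Kit in the past 2-8 complete months prior to study initiation". It assumes one cycle per month, purchase month even over 2-8 and planned use even up to the limit of 6, giving 25.5/25.5/18.3/13.6/10.0/7.1%.

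| Kit, mix | Constant: total, P | Beta, a + b = 5: total, P |
|---|---|---|
| 15%, 60% mix | 23.7%, 0.62 | 21.8%, 0.24 |
| 10%, window | 24.5%, 0.76 | 20.9%, 0.11 |
| 9%, window | 22.3%, 0.33 | 19.0%, 0.01 |

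With one cycle each, all three kits pass with probability near 0.

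**The documents' IUI figures against each other.** At a constant rate, 10% and 20% per cycle imply 1 − 0.90⁶ = 46.9% and 1 − 0.80⁶ = 73.8% over six cycles. Section 4.1 gives 10-35% across six, and 35% over six is 1 − 0.65^(1/6) = 6.9% per cycle. The figures do not agree.

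**A check on the obvious repair.** Pooled pregnancies/cycles equals r under a constant rate. If users differ, the more fertile conceive and leave. Under Beta(1,4) the ratio for a kit at 20% in the first cycle is 18.3% in the 60% mix (28.3%/1.544 cycles), 17.7% in a 40/25/15/10/5/5% mix, 17.2% in the window mix and 16.5% with use even over 1-6. In simulations of these four mixes, its 95% upper limit fell below 20% in about 21% to 87% of runs.

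**The case against.** *The denominator is not stated.* Section 8.3 reports infections per respondent and per cycle, and section 9.1 uses total cycles for insemination timing. If a per-cycle pregnancy rate was meant, the mismatch disappears. This stands as a limit on the point. The objective, endpoint and survey item are all per person, however, and section 9.1 would still need to say which is meant.

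*Multi-cycle use may be rare.* Section 2.3.2 says one kit serves two inseminations within a cycle, section 5 expects use within the month after purchase, and section 5.1 admits users of one cycle. This is fair, and is why no size can be claimed. Yet the endpoint and the survey both provide for up to six cycles.

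*The decision rule is not the plan's.* Section 9.1 names no test and quotes a range. Kits at 10-15% lie within that range, and a 20% kit does satisfy equivalent or better. This stands: the probabilities illustrate the bias and are not the plan's error rates. An informal comparison would carry the same bias.

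*Constant rates exaggerate.* Sections 3 and 4.2 expect fertility to vary by age, relationship and infertility source. The tables show that variation sharply reduces the figures for weaker kits, but it leaves the direction unchanged.

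*A six-cycle IUI figure exists.* Section 9.1 does not use it, and its unit conflicts between sections 2.2 and 4.1.

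**Conclusion.** The point holds on the natural per-person reading, and should be resolved before the data are analysed. Against the one-cycle 20% figure, the primary comparison is fair only if every respondent used one cycle; otherwise it favours the kit by a factor above 1 and at most 6. The exploratory model does not alter this. The size is undetermined. For a kit exactly at 20%, a fifth of users prepared to try a second cycle is enough, in the illustration, to raise a wrong declaration of better from 0.04 to 0.40-0.52.

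Three stronger readings are tempting, and the documents support none of them:
- A reader might infer that a kit clearly worse than IUI would usually pass. With no cycle distribution this cannot be said: a 9% kit in the window mix passes with probability 0.33 or 0.01, depending on the assumed spread of fertility.
- A reader might infer that all of 10-20% is a per-cycle range. Only the 20% end carries that unit.
- A reader might infer that the kit is favoured against any IUI figure. Against 10-35% across six cycles the direction can reverse: a kit at 6.9% per cycle, which reaches 35% over six, would show only 6.9% if everyone used one cycle.

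**What to change.** In section 9.1, state the denominator and compare like with like.

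1. Fix a one-cycle IUI reference before the data are opened: 20% as documented, and 10% only once its unit is confirmed. Compare it with the first-cycle pregnancy rate, or with pregnancies in kit cycles 1-6 divided by kit cycles 1-6 used, with a respondent-clustered 95% CI, or with both. Say in advance which is primary.
2. State that the pooled ratio falls as more cycles are used when users differ in fertility, so it matches the reference only if the IUI figure was pooled over a similar number of cycles.
3. Keep the total over up to 6 cycles as a descriptive result, reported with the distribution of cycles used, and do not compare it with a one-cycle rate.
4. Claim equivalence only with a margin stated in advance.
5. Reconcile the 10-35% figure in sections 2.2 and 4.1 before using it as a six-cycle benchmark.

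Appendix A already collects use by cycle up to 6. If no item in the figures not shown records the cycle of conception, add one (Appendix A allows questions to be revised) or state that the last reported cycle is taken as the cycle of conception.

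Cost: an amendment with IRB approval (Statement of Compliance) and possibly one survey item; no extra respondents. With 500 respondents, a first-cycle rate near 20% has a 95% half-width of 1.96 × √(0.2 × 0.8/500) = 3.5 points. The result will probably be less favourable to the kit, and the pooled ratio may understate the first-cycle rate.

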5.1 Inclusion Criteria

In order to be included in the study, the following inclusion criteria will be used.

Inclusion Criteria:

- Provide implicit consent by filling out and submitting the survey.
- Used a Mosie Kit to conceive during at least one cycle.
- At least 18 years old.
- Has an active email on file (presumed or they would not have received an invitation to participate. This information will not be verified as there is a desire to keep the survey completely anonymous.)

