[figure not shown]
How did you or your partner time your ovulation? (Select all that apply.) *
Count days in cycle
Track vaginal or cervical fluids
Tracking changes in the cervix
Use ovulation predictor kit
Use an app to estimate ovulation
Basal Body Temperature
Wearable device
Did not time ovulation
Did using Mosie result in a pregnancy? *
O Yes
O No
Back Next Page 10 of 20

[figure not shown]
Never submit passwords through Google Forms.

 $This \ content \ is \ neither \ created \ nor \ endorsed \ by \ Google. \ \underline{Report \ Abuse} - \underline{Terms \ of \ Service} - \underline{Privacy \ Policy}$

Google Forms

Page 56

[figure not shown]

Safe process

Enjoyable

	Very Easy	Easy	Neutral	Difficult	Very Difficult
To collect the semen/sperm sample in the cup?	0	0	0	0	0
To draw up the semen/sperm in the syringe?	0	0	0	0	0
Insert the Mosie syringe into the vagina up to the handles?	0	0	0	0	0
To deposit the semen/sperm at or near the cervix using the syringe?	0	0	0	0	0
My overall impression on the ease of use	0	0	0	0	0
					Page 12 of 20
submit passwords to	through Google Fo				

MOSIE-001 © 2020 Mosie Baby Page 59

MOSIE-001 © 2020 Mosie Baby

Page 60

Pulled the syringe plunger back and forth to confirm it was functioning.

My partner washed their hands

Use a sperm friendly-lubricant.

Thawed out donor sperm from sperm bank

Prepared all items and have them handy ready to use.

Washed the penis

that	apply)?*
	Lie down in a comfortable position.
	Relax
	Receive oral sex
	Stimulate clitoris
	Use any vibratory or non-vibratory stimulation device intravaginally
	Have an orgasm
	Other:
	erall, how well were you able to use the Mosie syringe to inseminate yourself our partner? * Very Able
	our partner? *
or y O O O	our partner? * Very Able Able Not Very Able
or y 0 0 0 0	Very Able Able Not Very Able Not Able at All Volume at All Volume at All Volume at All Volume at All Able at All Volume at All Able at All Able at All
or y O O O	Very Able Able Not Very Able Not Able at All Volong did you remain laying down after using the Mosie syringe? * Less than 15 minutes

Willelf best descri	ibes your lying position? *	
On my stomach	n	
On my side		
On my back		
On my back wit	th my hips elevated by a pillow	
Other:		
O No		
O		
What type of sam	ple did you use? *	
What type of sam	ople did you use? * rom a sperm bank (frozen)	
What type of sam	rom a sperm bank (frozen)	

0 2000	thank 50%	
O 51%-	70%	
O 71% -	80%	
O 81%-	90%	
O 90%-	95%	
O 96%-	100%	

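### The primary pregnancy rate is a crude total over users with one to six cycles of exposure, so it can be read neither as a 6-cycle rate nor as a per-cycle rate

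*Combined protocol and SAP*

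**What the plan says.** - **Endpoint.** Section 3 sets the primary endpoint as "Pregnancy Rate after up to 6 cycles" and explains the choice: "pregnancy rate in up to 6 (six) cycles will be examined as it is the typical standard timeframe".
- **Sample.** Section 5 takes "all individuals who have purchased the Mosie Kit in the past 2-8 complete months prior to study initiation", and adds that "complete months are used with the expectation that the Mosie Kit would be used within the month post-purchase". Under section 5.1 the exposure needed to enter is "Used a Mosie Kit to conceive during at least one cycle".
- **Measurement.** One anonymous survey, with no follow-up possible (section 4.3). The legible outcome item in Appendix A is "Did using Mosie result in a pregnancy", answered Yes or No. Appendix A also says that cycle pages 2 to 6 are skipped for a one-cycle user, so use is recorded by cycle.
- **Analysis.** The whole analysis given for Primary Hypothesis 1 in section 9.1 is a "Comparison of total rates of pregnancy using the Mosie Kit", set against a 10-20% IUI rate credited to the American Pregnancy Association.

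No section defines the denominator of this rate, says how a user still trying is handled, or plans a per-cycle or cumulative estimate for the primary endpoint. Number of cycles meets pregnancy outcome only in the exploratory model of section 9.4.3.

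**The concern.** A respondent in her second cycle and one who has failed six cycles both answer No and carry equal weight. The total is then an average of one-, two-, up to six-cycle risks. Its weights depend on when people bought, how often they bought again, when they stopped and when they answered the survey. None of these is a property of the kit.

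Two readings of the result are at stake. Against a rate over six cycles, such as the 10-35% in section 4.1, the total is biased low. Against a one-cycle rate, such as the figure of up to 20% in the same paragraph, it is biased in the kit's favour. Section 9.1 does not say how many cycles its 10-20% range covers. The mix would also move if collection is extended (up to 90 days, section 10.1.2) and newer purchasers are invited (section 5).

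**Working it through.** **1. The plan's own figure.** Section 9.2: half-width = 1.96 × √(0.25/n). For n = 500 this is 4.38%, and for n = 384 it is 5.00%. Both stated margins reproduce. They describe sampling error only.

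**2. Who has had time for six cycles?** Assumed, because the documents do not give it: purchases evenly spread over months 2 to 8; cycle length of 28 days (six cycles = 5.52 months) or one month (six cycles = 6 months); delay *d* from purchase to first use of 0 or 1 month (section 5). With *r* the months from study start to response:

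share short of six cycles = (length of six cycles + d − 2 − r) / 6

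- Study start, lowest: (5.52 + 0 − 2)/6 = 59%. Highest: (6 + 1 − 2)/6 = 83%.
- Day 30 (r = 1): (5.52 − 3)/6 = 42% to (7 − 3)/6 = 67%.
- Same purchasers at three months (r = 3): (5.52 − 5)/6 = 9% to (7 − 5)/6 = 33%.

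**3. Effect on the total.** Per-cycle rate p = 10% or 15% (the ICI/IVI range in section 2.2), taken as constant across users and cycles. With s the share stopping after each failed cycle and q = (1 − p)(1 − s), the chance of pregnancy within k available cycles is p(1 − q^k)/(1 − q). With s = 0 this is 1 − (1 − p)^k. For p = 10% and k = 1 to 6 it gives 10.0, 19.0, 27.1, 34.4, 41.0 and 46.9%.

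The crude total is the mean over the seven purchase months 2, 3, …, 8. The three columns take k = 1,2,3,4,5,6,6 (A), k = 2,3,4,5,6,6,6 (B), and one further month of exposure, k = 3,4,5,6,6,6,6 (C).

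| p | s | A | B | C | All with six cycles available |
|---|---|---|---|---|---|
| 10% | 0 | 32.2% | 37.4% | 41.4% | 46.9% |
| 15% | 0 | 44.2% | 50.9% | 55.9% | 62.3% |
| 10% | 30% | 20.6% | 22.8% | 24.1% | 25.3% |
| 15% | 30% | 29.4% | 32.3% | 33.9% | 35.4% |

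Shortfall with no stopping: 9.4 to 18.1 points in A and B, and 5.5 to 6.4 in C. With 30% stopping (an assumed value): 2.5 to 6.0 points in A and B, and 1.2 to 1.5 in C. A finer calculation over the ranges in step 2, with no stopping, gives 9 to 21 points at study start and 5 to 13 at one month.

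**4. Direction against a one-cycle benchmark.** A kit with a true 10% per cycle has half the one-cycle IUI figure of 20% in section 4.1. With no stopping its crude total would be 32-37% (A and B), which looks clearly better.

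**5. Does the alternative work?** In data simulated with 28-day cycles, no delay and no stopping, the crude totals were 37.5% and 51.1%. A discrete life table censored at the last completed cycle gave 46.9% and 62.3%, matching 1 − (1 − p)^6.

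**The case against.** **The wording allows fewer than six cycles.** This stands. A proportion among people with one to six cycles of natural use is not contradicted by the endpoint's words. A reader might infer that the plan promises a 6-cycle rate and then breaks the promise. The documents do not support that. The fault is that the estimand and its denominator are left undefined, while the six-cycle justification and an across-six-cycles benchmark invite that reading.

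**The exposure figures are assumed.** This stands. A reader might infer that most purchasers are known to lack six cycles. Purchase dates are not given, and the share falls to 42-67% by day 30 and lower for late answers. Nor is the total fixed by sales dates alone. One kit serves about one cycle (section 2.3.2), so rebuying and stopping matter too, and users who first bought before the window have more exposure.

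**The gap may be small.** Partly stands. With 30% stopping it is around or below the ±4.4 points. Real variation in fertility between users would shrink it further. The blending remains, however, and its size cannot be seen from the total.

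**The conclusion on Hypothesis 1 may not change.** With no stopping, both the crude total and the 6-cycle rate exceed 20%. A reader might infer that the test result would be wrong; that is not shown. What is lost is the interpretation.

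**The survey is only partly readable.** That those still trying count as non-pregnant is inferred from the Yes/No item and the total rate. A reader might also infer that pregnancies after cycle 6 enter the rate. The pages that would show this are not legible, so that claim is not made.

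**Conclusion.** The concern holds in this form: as planned, the primary rate is a blend over unequal exposure and supports neither a 6-cycle nor a per-cycle statement. Its distance from the 6-cycle rate is about 9 to 18 points at study start with no stopping. Its distance from what the same users would show with full follow-up is about 1 to 6 points with 30% stopping after each failed cycle. These sizes rest on even purchase dates, roughly monthly cycles, a constant 10-15% per cycle and an assumed stopping rate. A larger sample would not reduce the error. The direction of the bias depends on the benchmark, so the total should be called neither conservative nor favourable until the number of cycles behind the IUI figure is fixed.

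**What to change.** In section 9.1:

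1. Make the primary estimate the discrete life-table cumulative pregnancy probability by cycle 1 to 6, with per-cycle rates, from the cycle pages already in the survey. Censor No respondents at their last completed cycle.
2. Compare it only with a benchmark over the same number of cycles.
3. Add three separate response options: *current cycle, result not yet known*; *still trying with the kit*; *stopped using the kit*. Confirm that the form identifies the cycle of conception.
4. Because stopping may be related to prognosis, report bounds: stoppers censored (upper, if they are no more fertile than those who continue) and stoppers treated as not conceiving through cycle 6 (lower). In the illustration with 30% stopping these would be 46.9% and 25.3% at p = 10%, and 62.3% and 35.4% at p = 15%.
5. Keep the crude total as descriptive, beside the distribution of cycles used.

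**Cost.** Three response options and a few lines of text; Appendix A already allows questions to be revised. It must be done before launch, because an anonymous one-time survey cannot be queried later. Intervals will be wider at cycles 5-6, the ±4.4% will not apply to the 6-cycle estimate, and the bounds may be far apart.
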